### 6.4 STUDY INTERVENTION COMPLIANCE

The Investigator is responsible for ensuring that the treatment and follow-up procedures are followed as laid out in this protocol, unless a deviation is needed to protect the health and welfare of a subject. Such deviations should promptly be reported to the Sponsor or their designee and may also require reporting to the IRB.

Protocol compliance by the Investigator and site staff will be monitored by routine site visits conducted by the Sponsor, the frequency of which will be determined by any findings of issues as outlined in a separate detailed monitoring plan. All subjects will be provided with instructions which may include written materials on how to off-load correctly. Subject compliance will be based on observation of the offloading device at each visit for evidence of wear, by queries regarding excluded concomitant medications / therapies, and queries regarding dosing of any antibiotics. No blood testing or other test procedure will be utilized for determination of compliance. Diaries will not be used.

## 6.5 CONCOMITANT THERAPY

Systemic anti-microbials may be used as prescribed. Wound cleansing with a neutral, non-irritating and non-toxic solution is recommended at the discretion of the Investigator. Sterile saline, non-ionic cleanser, or hypochlorous acid are recommended.

Canagliflozin, a type 2 diabetic medication, also referred to as Invokana, Invokamet, and Invokamet XR, is not permitted throughout the duration of the screening, treatment and confirmation of closure periods.

Concomitant therapies for treating the index ulcer other than those defined in the protocol will not be permitted during the treatment and confirmation of closure period. They include topical antibiotics, antiseptic agents including hydrogen peroxide, acetic acid, chlorhexidine, povidone/iodine, and cetrimide, enzymes, negative pressure wound therapy, hyperbaric oxygen, growth factors, living skin, dermal substitutes, silver-containing products, amniotic membrane or umbilical cord products or other advanced biological therapies, or revascularization procedures (e.g., endoscopic perforator surgery, superficial venous ablation, endovenous laser ablation, valvuloplasty, free flap transfer with microvascular anastomoses), and Achilles tendon lengthening.

### 6.5.1 RESCUE MEDICINE

Not applicable.

## 7 STUDY INTERVENTION DISCONTINUATION AND PARTICIPANT DISCONTINUATION/WITHDRAWAL

### 7.1 DISCONTINUATION OF STUDY INTERVENTION

Given that the manufacturing method of the test article is similar to the commercial product NEOX® CORD 1K®, which has an outstanding safety record, there is no *a priori* expectation of needing to suspend or terminate the trial for unexpected adverse events.

### 7.2 PARTICIPANT DISCONTINUATION/WITHDRAWAL FROM THE STUDY

All subjects have the right to discontinue the trial at any time. The Investigator may also withdraw a subject from the trial at any time if they deem it medically necessary. The reason for discontinuation should be documented and trial staff should attempt to bring the subject in for an Early Termination Visit and perform all applicable assessments as appropriate listed under the End of Treatment Period Visit (Visit 19) for discontinuations that occur during the Treatment Period.

Subjects may be discontinued from the trial for the following reasons:

- Adverse Event (including illness)

- Subject withdrawal of consent
- The Sponsor or Investigator terminates the trial
- Lost to follow-up
- Product-related > Grade 2 skin or systemic allergic reaction
- Ulcer-related complications (i.e., life-threatening, infection-related sepsis complications)
- Subsequent limb amputation (i.e., full amputation involving the index ulcer anatomic location)

In the event of a subject's withdrawal, the Investigator will promptly notify the medical monitor and will make every effort to complete all procedures at either the End of Treatment Period Visit. Even if removed subjects have been removed from the trial or if an adverse event remains ongoing, Investigators should follow up with subjects as per their standard medical practice.

Discontinued subjects will not be replaced. Simultaneous screening at multiple sites may result in an allowable modest over-enrollment.

### 7.3 LOST TO FOLLOW-UP

If a subject is lost to follow-up, a minimum of three documented contact attempts including one certified letter should be in the records. If there is not contact made by the subject after sending the certified letter, the next of kin and the physician responsible for managing the subject's diabetes should be contacted to obtain information about the subject's current health status.

## 8 STUDY ASSESSMENTS AND PROCEDURES

### 8.1 STUDY ACTIVITIES BY VISIT

#### 8.1.1 SCREENING PERIOD (WITHIN -7 DAYS FROM INITIAL PROCEDURE VISIT)

[Purpose]: To determine the trial eligibility by assessing all inclusion/exclusion criteria based on the medical information available, clinical assessment, clinical laboratory testing, imaging studies and interview with subject.

Each subject who enters Screening will be assigned a subject ID number for traceability. The subject ID will consist of a 2-digit site number and a 3-digit subject number (i.e. 01-001, etc.).

Any subject who signs an informed consent, but fails to meet the required eligibility criteria is considered to be a Screen Failure. Screen Failure subjects should have their demographic information captured with the reason for screen failure specified. If a subject fails to meet all criteria after two screening attempts, the subject may not be enrolled into the trial. A new informed consent is required for each screening attempt. All procedures, excluding qualifying lab and

vascular perfusion tests obtained within 30 days of re-screening, must be repeated for each screening attempt.

All subjects will be screened for trial eligibility using the following procedures. All procedures must be completed prior to the Initial Procedure Visit:

This figure is a 2D grayscale heatmap representing a complex, multi-peaked distribution. The distribution is highly concentrated in the center, with several distinct peaks of varying intensities extending towards the edges. The background is dark, and the peaks are bright white and light gray. The distribution is roughly rectangular in shape but with irregular, jagged edges, suggesting a noisy or high-resolution data set.

#### 8.1.3 TREATMENT PERIOD [VISIT 01 THROUGH VISIT 15 (7 +/- 2 DAYS)]

[Purpose]: To monitor safety and wound healing, adjust antibiotic regimens, and administer treatment. At each visit of Visits 01 through 15, if the wound is found to be open, the listed procedures will be performed for the subject.

If the index ulcer is observed to be closed, the subject will continue immediately to Treatment Period Visit 16 and complete all of the procedures listed under Visit 16.

[figure not shown]
If the subject will discontinue from treatment at any of these visits, the subject should move immediately to the end of Treatment Period Visit (Visit 19) and complete all of the procedures listed under Visit 19.

[figure not shown]

[figure not shown]
**Figure 3. Treatment if there is no SSTI observed**

**Figure 4. Treatment if SSTI is observed without recurrence of clinical suspicion of osteomyelitis**

**Figure 5. Treatment if SSTI is observed with clinical suspicion of osteomyelitis**

---

#### 8.1.4 TREATMENT PERIOD [VISIT 16 (7 +/- 2 DAYS)]

[Purpose]: To document the index ulcer status of open versus closed.

If a subject's wound is judged to have not closed at this visit the subject will not complete the procedures for this Visit, but will move immediately to complete the End of Treatment Visit (Visit 19) procedures.

If the index ulcer is observed to be closed prior to or at this visit, the following procedures will be completed and the subject will be instructed to return for the Confirmatory Period Visit 17 in (7 +/- 2 days).

[figure not shown]
---

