### 3 OBJECTIVES AND ENDPOINTS

OBJECTIVES	ENDPOINTS	JUSTIFICATION FOR ENDPOINTS
Primary		
To examine the safety and estimate the efficacy of TTAX01 plus standard care (SC) in achieving complete wound healing of complex non-healing diabetic foot ulcers with high risk factors of [1] ulcer depth indicating exposed bone, tendon, muscle, and/or joint capsule and [2] clinical suspicion of osteomyelitis	Proportion of subjects with complete wound healing over the 16-week treatment period, defined as complete epithelialization with no drainage and no need for a dressing, confirmed at two visits, two weeks apart, and a biweekly end of treatment visit for a confirmatory duration of 4 weeks	Per FDA 2006 Guidance on endpoints for wound healing trials
Secondary		
To examine additional efficacy endpoints related to wound healing	
 
• Time in number of days to complete wound closure over the 16-week treatment period, starting from enrollment to the time of the initial observation of wound closure
 
• Proportion of subjects with complete wound closure at each of the 16 treatment weeks
 
• Percent change in the wound surface area (<math>\text{cm}^2</math>) at each visit from baseline for assessing the rate of wound closure in area
 
• Percent change in the wound volume (<math>\text{cm}^3</math>) at each visit from baseline for assessing the rate of wound closure in volume
 
• Percent change in the wound depth (cm) at each visit from baseline for assessing the rate of wound closure in depth
 
• Percent of index wound covered by the granulation tissue at each visit for assessing the rate of wound closure in granulation tissue
 
• Proportion of subjects achieving complete wound closure in subjects with pathologically confirmed osteomyelitis
 
	Time to heal is an alternative endpoint per the 2006 Guidance  Typical alternative to Cox proportional hazard  Wound area reduction may allow surgical closure  Alternate view of healing progress  Alternate view of healing process  Alternate view of wound healing process  Subset analysis
To examine the effect of therapy on ulcer-related complications (safety)	• Proportion of subjects who experience ulcer-related complications (e.g., life-	Relevant safety measures

OBJECTIVES	ENDPOINTS	JUSTIFICATION FOR ENDPOINTS

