### 8.2 EFFICACY ASSESSMENTS

At each of the Treatment Period visits (1 – 16), the Investigator will make a determination as to whether the wound has healed completely. If complete healing is observed, the subject will be scheduled to return in one week for Visit 17. During that week, the Investigator must confer with the independent reviewers to assure concordance of opinion regarding closure. Should it happen that the independent reviewers judge the wound to be unhealed, the subject will be rescheduled to attend the next regular Treatment Period visit instead of Visit 17.

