4.5.2 Results of secondary efficacy analyses

Descriptive and inferential statistics on the ITT population of the number of days to complete ulcer closure will be presented in Table 2.3.1 for Cox regression analysis. The resultant probability of subjects with index ulcer open over the 16-week treatment period and estimated median time to ulcer closure will be reported in Table 2.3.2. For the PP population, the results of the same Cox regression analysis on the number of days to complete ulcer closure will be presented in Table 2.3.3 and Table 2.3.4.

Descriptive and inferential statistics on the ITT population of the proportion of subjects with complete ulcer closure for each post-baseline treatment week will be presented in Table 2.1.1.

Descriptive and inferential statistics on the ITT population of percent change of index ulcer parameters (ulcer area, depth, and volume) and percent of granulation tissue coverage at each treatment visit will be presented in Tables 2.4.1 thru 2.4.4.

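### Visit 16 and Visit 19 labels depend on whether the ulcer has closed, so the four by-visit wound measures need to be summarised by study week

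*Protocol*

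**What the plan says.** **Routing.** Protocol 8.1.3 carries out the procedures of Visits 01 to 15 when the wound is open, and adds: "If the index ulcer is observed to be closed, the subject will continue immediately to Treatment Period Visit 16". Protocol 8.1.4 gives the purpose of Visit 16 as "To document the index ulcer status of open versus closed". For an ulcer not closed by then, "the subject will not complete the procedures for this Visit, but will move immediately to complete the End of Treatment Visit (Visit 19". Visit 19 is also used after a re-opening (Protocol 8.1.5), for early discontinuation (Protocol 8.1.3, SAP 2.2), and two weeks after Visit 18 for confirmed closures (SAP 2.2).

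**Closure status.** Protocol 8.2 states: "At each of the Treatment Period visits (1 – 16), the Investigator will make a determination as to whether the wound has healed completely". If the independent image reviewers overrule a closure, "the subject will be rescheduled to attend the next regular Treatment Period visit instead of Visit 17".

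**Endpoints.** Protocol section 3 defines percent change in area "at each visit from baseline for assessing the rate of wound closure in area", with parallel definitions for volume and depth, and percent granulation also by visit. The closure endpoint beside them is indexed by week: "Proportion of subjects with complete wound closure at each of the 16 treatment weeks". SAP 4.5.2 follows the by-visit form for the wound measures: "percent of granulation tissue coverage at each treatment visit will be presented in Tables 2.4.1 thru 2.4.4".

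**SAP visit text.** SAP 2.2 lists Visit 16 among the visits at which status and size are assessed for each subject, and sends early closers to Visits 17 and 18 without mentioning a Visit 16. SAP 2.3 has ulcer measurements taken at every visit from 01 to 19, with windows of ±2 days referenced to the Initial Procedure Visit. The handling rules for these measures (SAP 2.8) and the secondary analysis (SAP 2.9.2) are redacted.

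**The concern.** A by-visit summary is readable as a healing curve only if each visit number stands for one study time and every subject still under observation can appear in it. Under the protocol's routing neither holds for the late visits. A subject's record falls under Visit 15, 16 or 19 according to whether and when the ulcer closed.

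If the tables group records by nominal label, the Visit 15 summary describes ulcers that have not healed. The Visit 16 summary describes ulcers judged healed, at any week. The week-16 measurements of open ulcers, taken under Visit 19 procedures, may fall outside the treatment-visit tables altogether. Four secondary measures are exposed. The pilot is meant to expose contradictions in its own protocol (Protocol 8.5.1) and to give a response estimate for a larger trial (Protocol 2.1 and 4.2), so this is the place to settle it.

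**Working it through.** **1. The plan's own timeline.** Screening 1 + treatment 16 + Visits 17 and 18 2 + Visit 19 2 = 21 weeks, which matches the maximum participation in Protocol 1.1. The nominal calendar is coherent, and the difficulty is only in how labels attach to it.

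**2. Labels mapped to study weeks.** For an ulcer that closes at week w, applying Protocol 8.1.3 to 8.1.6 and SAP 2.2, and ignoring the ±2-day window:

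| Label | Who | Study week |
|---|---|---|
| Visit 16 | Judged closed by the investigator | w, so 1 to 16 |
| Visit 17 | Same | w + 1, so 2 to 17 |
| Visit 18 | Same | w + 2, so 3 to 18 |
| Visit 19 | Confirmed closure | w + 4, so 5 to 20 |
| Visit 19 | Re-opened at Visit 17 or 18 | 2 to 18 |
| Visit 19 | Open at Visit 16 | 16 |
| Visit 19 | Early termination | week of leaving |

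Only the row for ulcers open at Visit 16 is tied to week 16.

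**3. How many Visit 16 records would come from week 16 (illustration).** Assumptions: 36 subjects (the planned number), no dropout, a constant weekly closure hazard, and a proportion p closed by week 16. The hazard is h = 1 − (1 − p)^(1/16). The share of closers who close before week 16 is [1 − (1 − h)^15] / p.

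| p | Visit 16 records (36 × p) | Share before week 16 | Mean closure week |
|---|---|---|---|
| 0.3 | 10.8 | 94.7% | 8.0 |
| 0.5 | 18.0 | 95.6% | 7.6 |
| 0.7 | 25.2 | 96.7% | 6.9 |

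**4. Effect on mean percent area reduction (illustration).** The documents give no closure rate or shrinkage for this trial, so both are assumed. Let r be the mean reduction in ulcers still open. The all-subject week-16 mean is M = p × 100 + (1 − p) × r.

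- p = 0.5, r = 40: 0.5 × 100 + 0.5 × 40 = 70%.
- p = 0.4, r = 30: 0.4 × 100 + 0.6 × 30 = 58%.
- p = 0.6, r = 50: 0.6 × 100 + 0.4 × 50 = 80%.
- Wider range: p = 0.3, r = 30 gives 51%; p = 0.7, r = 70 gives 91%.

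By nominal label, Visit 15 would show about r (40% in the first case) because its procedures are for open ulcers. Visit 16 would show about 100% whatever p and r are. It is not exactly 100%, because an overruled closure can leave a Visit 16 record for an ulcer later ruled open.

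**5. Protocol against SAP.**

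| Question | Protocol | SAP |
|---|---|---|
| Visit 16 for an open ulcer | Visit 19 procedures instead (8.1.4) | Status and size for each subject (2.2); measurements at every visit (2.3) |
| Next step for an early closer | Visit 16 (8.1.3) | Visits 17 and 18, Visit 16 not mentioned (2.2) |

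SAP 2.6 also calls baseline Visit 01, whereas SAP 2.2 and 2.3 call it Visit BS.

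**The case against.** The strongest reply is that the distortion arises only if raw records are grouped by nominal label, and the text that would say so cannot be read. SAP 2.8 has a heading for exactly these measures, and its content is redacted, as is SAP 2.9.2. Visible text hints at some handling: Listing 6 (SAP 4.5.1) gives area and closure status by visit with and without imputation, LOCF and worst-case appear among the abbreviations, and visit windows are anchored to baseline. This stands. A mapping or carry-forward rule cannot be called absent, nor can it be said that the hidden text fails to cure the problem.

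A reader might also infer that no Visit 16 data exist for open ulcers. The documents do not support that. Visit 16 exists to record open or closed, the investigator determines healing at every treatment visit, and the SAP expects status and size for each subject. What the protocol restricts is completion of the Visit 16 procedures. It does not say under which label the database stores the week-16 measurement of an open ulcer.

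Nor is it shown that the SAP tables contain a mixed Visit 19 column, since they are by treatment visit and SAP 2.2 places Visits 17 to 19 in the confirmatory period. Finally, the percentages above are assumptions, so they show the mechanism and do not predict a result.

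None of this removes the core: the readable routing rules make the label depend on outcome, and the readable endpoint and table definitions use the label.

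**Conclusion.** The point holds in conditional form. Visit 16 procedures are completed only for ulcers the investigator judges closed, at any of weeks 1 to 16, and ulcers open at week 16 receive Visit 19 procedures. Four secondary measures are nevertheless defined and tabulated by visit. If nominal labels drive the analysis, the late-visit summaries are selected on outcome and mix study times. In the illustration a true all-subject mean of 70% (58% to 80% over the stated range) would appear as about 40% and about 100% under adjacent labels.

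The reach is limited. This is a single-arm, descriptive pilot. Weekly closure is indexed by treatment week and time to closure is in days, so neither need be affected, and nor need the primary endpoint. A reader might conclude that the whole healing trajectory is uninterpretable, but that goes further than the documents allow while the handling rules are redacted. The disagreement between Protocol 8.1.3 and 8.1.4 and SAP 2.2 and 2.3 does not depend on redacted text and needs resolving in any case.

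**What to change.** - In Protocol section 3 and SAP 4.5.2, define the four measures and Tables 2.4.1 to 2.4.4 by study week, computed from actual days since Visit BS.
- Assign week-16 measurements of open ulcers taken under Visit 19 procedures to week 16, and early Visit 16 records to the week in which they were taken.
- Count area, depth and volume as zero after confirmed closure. Use observed values after a re-opening or an overruled closure. State how percent granulation is counted once an ulcer has closed.
- Reconcile Protocol 8.1.3 and 8.1.4 with SAP 2.2 and 2.3 on who is assessed at Visit 16 and which visit follows an early closure, and use one name for baseline throughout the SAP.
- If the redacted SAP text already contains these rules, it is enough to align the by-visit wording of Protocol section 3 and SAP 4.5.2 with them.

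The cost is wording changes and a date-based mapping step in programming. No new data or visits are needed.

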#### 8.1.5 CONFIRMATORY PERIOD [VISIT 17 AND VISIT 18 (7 +/- 2 DAYS)]

[Purpose]: To confirm complete wound healing for those who demonstrate wound closure during Treatment Period by two consecutive visits, one week apart, providing a total of two observations two weeks apart.

If a subject's ulcer is judged to have re-opened at this visit the subject will not complete the procedures for this Visit, but will complete the End of Treatment Period Visit (Visit 19) procedures.

#### 8.1.6 END OF TREATMENT PERIOD VISIT (VISIT 19) (14 +/- 2 DAYS)

[Purpose]: To document the patient status if they complete the entire treatment period or if they are withdrawn from the study during this period.

### 8.2 EFFICACY ASSESSMENTS

At each of the Treatment Period visits (1 – 16), the Investigator will make a determination as to whether the wound has healed completely. If complete healing is observed, the subject will be scheduled to return in one week for Visit 17. During that week, the Investigator must confer with the independent reviewers to assure concordance of opinion regarding closure. Should it happen that the independent reviewers judge the wound to be unhealed, the subject will be rescheduled to attend the next regular Treatment Period visit instead of Visit 17.

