## 4 STUDY DESIGN

### 4.1 OVERALL DESIGN

The hypothesis under study is that one or more applications of TTAX01 to the wound surface of a well debrided, complex diabetic foot ulcer managed with appropriate antibiotic therapy will result in a higher probability of complete healing than would be expected from management with standard care alone. In this open label Phase 2 pilot trial, all subjects will receive the intervention over a maximum period of 16 weeks. Eligible consenting subjects will undergo a baseline aggressive debridement in the operating room to remove infected and devitalized bone and soft tissue. A six week course of systemic antibiotics will be used to resolve baseline infection. TTAX01 will be applied to the debrided wound bed at baseline, and if healing is not evident, it will be applied again at 4 week intervals. At each weekly visit the wound will be further debrided as necessary.

To reduce bias in the ascertainment of complete closure, one independent observer will review the image obtained from a wound measurement device (eKare inSight™) in each case where the Investigator makes a determination of closure. Discordant opinions will be adjudicated by a third independent reviewer who will examine multiple additional images taken at various angles to the wound surface.

Bias will be further controlled by distributing enrollment over approximately twelve clinical sites. Because all subjects will receive the intervention, there will be no stratification on variables known to influence the probability of healing (e.g., wound size, wound duration, gender). No interim analysis is planned, but an ongoing review of protocol compliance may lead to amendments where it is determined that additional clarity is needed. It is expected that operational issues with this protocol will be worked through in anticipation of designing a similar, pivotal Phase 3 trial.

Consenting subjects who qualify for enrollment will undergo an aggressive surgical debridement at the baseline visit, including biopsies of bone for histology and microbiologic testing at the start

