## 4.2 SCIENTIFIC RATIONALE FOR STUDY DESIGN

The prospective, multi-center design of this trial should serve to reduce selection and ascertainment bias compared with retrospective case series reported by individual clinicians. The design is expected to yield a more accurate estimate of response rates for the population under study, which can be used for statistical power calculations of a larger controlled trial. The open label design allows the Sponsor to immediately consider the relationship between treatment emergent adverse events and the test article, against the background of anticipated adverse events in this population.

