### 6.3 MEASURES TO MINIMIZE BIAS

The trial is open label, with no blinding of the site staff. All eligible subjects will be enrolled into a single active treatment arm. The determination of wound closure will be made by the Investigator based on visual and tactile assessment of the wound. High quality photographic images will be taken at each visit, from an angle and distance recommended for optimum computerized calculation of wound area. In the event that the Investigator determines that a wound is completely healed, several additional images will be acquired at different angles in order to observe surface reflection of light from newly formed epithelium, and the absence of exudate. An independent reviewer will examine the first photographic image in order to make a determination of wound closure. If this opinion is concordant with the Investigator's opinion, the wound will be recorded as healed. If the independent reviewer finds reason to disagree with the Investigator, a third independent reviewer will examine all of the photographs for the purpose of breaking the tie.

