Subjects' identified index ulcer will be assessed over the course of the treatment visits (Visit BS and Visits 1 through 16) or until their ulcers close. Subjects whose ulcers have closed, as assessed by the investigator and verified by an independent blinded evaluator using the images collected via the electronic wound imaging and measurement device, prior to the 16th week of treatment (or Visit 15) will stop treatment and return for two consecutive weekly visits (i.e., Visits 17, and 18) to verify if the target ulcer remains closed at these two visits following the initial observation of ulcer closure, which is defined as the complete ulcer closure in this study. Two weeks after the 2nd confirmatory visit (Visit 18), subjects with index ulcer remained as closed at Visits 17 and 18 will return and complete an End of Treatment Period visit (Visit 19). Subjects whose ulcers have not closed at the end of the 16-week treatment (i.e., Visit 16) or whose ulcers have re-opened during the confirmatory visits (Visits 17 and 18) will move on directly to complete the assessments of Visit 19. Visit 19 will serve as the study's End of Treatment (EOT) visit for the treatment and ulcer closure confirmatory period and will also serve as study exit visit.

For those subjects who are enrolled and discontinue from the treatment prior to Visit 16 due to any reasons other than target ulcer closure, Visit 19 will serve as the early termination (ET) visit.

The total duration of study starting from enrollment to the end of the treatment period is 16 weeks, during which time adverse events and ulcer-related complications, including limb amputation are assessed.

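### Protocol 8.2 has the unblinded Investigator confer with the image reviewers before Visit 17; as worded, a disagreement over closure can be settled by discussion without reaching the third-reader tie-break

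*Protocol*

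**What the plan says.** Protocol 6.3 states that site staff are not blinded and that the Investigator decides closure by looking at and touching the wound. An independent reviewer then reads the first photograph. On agreement: "If this opinion is concordant with the Investigator's opinion, the wound will be recorded as healed". On disagreement, "a third independent reviewer will examine all of the photographs for the purpose of breaking the tie". Protocol 4.1 gives the same rule ("Discordant opinions will be adjudicated by a third independent reviewer") and presents it as a way to reduce bias in ascertaining closure. Only cases that the Investigator has called closed are reviewed.

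Protocol 8.2 covers the week between the closure call and Visit 17: "During that week, the Investigator must confer with the independent reviewers to assure concordance of opinion regarding closure". The next sentence begins "Should it happen that the independent reviewers judge the wound to be unhealed" and sends such a subject back to the next regular treatment visit. Section 8.2 does not mention the third reviewer and does not refer to 4.1 or 6.3.

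SAP 2.2 describes closure "as assessed by the investigator and verified by an independent blinded evaluator using the images collected". It mentions neither conferral nor a third reader.

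Protocol 4.2 says the design should give a more accurate response estimate, "which can be used for statistical power calculations of a larger controlled trial".

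**The concern.** Agreement has two functions in 6.3: it records the wound as healed, and it means no third read takes place. Section 8.2 makes contact between the unblinded Investigator and the reviewers mandatory, and gives that same agreement as its purpose. If the reviewer has not yet committed to a read, a site can follow 8.2 to the letter, discuss a doubtful case until opinions match, and record agreement under 6.3. No deviation arises and adjudication is never triggered.

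The image read is the stated check on an open-label judgement that feeds the primary endpoint, and it works only if a disagreement is allowed to stand. The more worrying direction is upward. Because only closure calls are reviewed, a reviewer who is persuaded can only add healed subjects. The response estimate may be used to power a later trial, and the pilot is meant to rehearse the procedures of a similar Phase 3 trial, so the wording could be carried forward.

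**Working it through.** **Reading the texts together**

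| Step | Protocol 4.1 and 6.3 | Protocol 8.2 | SAP 2.2 |
|---|---|---|---|
| First independent read | One reviewer, from the image | Reviewers (plural), through conferral | One blinded evaluator, from images |
| Read recorded before contact | Not stated | Not stated | Not stated |
| If opinions agree | Recorded as healed | Visit 17 | Closure verified |
| If opinions differ | Third reviewer decides | Not stated; an unhealed verdict returns the subject to treatment visits | Not stated |

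The gap is the second row. With no order fixed, the 8.2 contact may come before the read that 6.3 relies on.

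**Scale**

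The plan gives no disagreement or overturn rate, so there is no figure to reproduce. One subject in 36 is 1/36 = 2.8 points.

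**Illustration (every rate is an assumption)**

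Let p be the true closure proportion, f the proportion of unhealed wounds called closed by the Investigator, d the chance that a reader rejects a false call, and w the chance that a reader rejects a true closure. Readers are taken to err independently.

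- Process in 6.3 (a call falls only if both readers reject it): p(1 − w²) + (1 − p)f(1 − d²)
- Reviewers always give way: p + (1 − p)f
- Investigator always gives way to the first reader: p(1 − w) + (1 − p)f(1 − d)

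With p = 0.50 and d = 0.80:

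| f | w | Process in 6.3 | Reviewers give way | Difference |
|---|---|---|---|---|
| 0.10 | 0.10 | 0.495 + 0.018 = 51.3% | 55.0% | +3.7 points (0.037 × 36 = 1.3 subjects) |
| 0.05 | 0 | 0.500 + 0.009 = 50.9% | 52.5% | +1.6 points |
| 0.20 | 0.10 | 0.495 + 0.036 = 53.1% | 60.0% | +6.9 points |

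In the first row, 0.5 of the 3.7 points (p·w² = 0.50 × 0.01) is true closures no longer wrongly rejected. The other 3.2 points ((1 − p)·f·d² = 0.05 × 0.64) are false closures let through.

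**Allowing for the confirmatory visits**

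If half the false calls in the first row fail at Visits 17–19, f is in effect 0.05 with w = 0.10. The process in 6.3 gives 0.495 + 0.009 = 50.4%, against 52.5% if reviewers give way. The difference is +2.1 points, or 0.021 × 36 = 0.8 of a subject.

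**A second set of assumptions**

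Take m closure calls, first-reader disagreement g, and a third reader who upholds half of the ties. Settling every tie as healed adds m·g·0.5/36. With 18 calls and g = 10% this is 2.5 points; with 30 calls and g = 30% it is 12.5 points. The result depends on the assumptions, so none of these values is an estimate.

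**The downward direction**

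In the first row, an Investigator who always gives way to the first reader gives 0.450 + 0.010 = 46.0%, which is 5.3 points below 51.3%. Of this, p(w − w²) = 0.50 × 0.09 = 4.5 points are truly closed wounds that the first reader wrongly rejected. Under 8.2 these subjects come to the next weekly visit and can be called closed again. The remaining 0.018 − 0.010 = 0.8 points are false closures removed, which is not a harm.

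A lasting loss is therefore mainly confined to closures first called at treatment Week 16, when no regular treatment visit remains. The visit label does not pick these out, because after any earlier closure "the subject will continue immediately to Treatment Period Visit 16".

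**The case against.** The strongest reply is that 8.2 is a scheduling paragraph. Conferring may mean no more than obtaining the result in time to book Visit 17, and the plural reviewers can include the third reader. The rules in 4.1 and 6.3 are mandatory and nothing in 8.2 suspends them. The read order may also be set in text that cannot be seen: the schedule in 1.3, the visit procedures in 8.1.3 to 8.1.5, or SAP 2.6.1 and 2.9.1. SAP 2.2 is only a design summary, so its silence on the tie-break shows little. All of this stands, and it limits the point to ambiguous wording. It does not remove the point, because the visible sentence in 8.2 names agreement as the aim of the contact, and about twelve sites would each have to choose the harmless reading.

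A reader might infer three stronger things that the documents do not support:

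- That 8.2 contradicts or cancels the tie-break. It does neither, since 4.1 and 6.3 state no recording order for 8.2 to breach.
- That the Investigator can overrule the reviewers. The sentence after the conferral instruction keeps an unhealed verdict available.
- That no trace of a settled disagreement could exist. The visible text requires no record of the read before discussion, but forms and procedures are not all shown. Photographs are taken at every visit, with extra views at a closure call, so a later re-read appears possible.

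**Conclusion.** The point holds as a wording gap in the bias control on the primary endpoint. As written, 8.2 permits a disagreement to be settled by discussion before the independent read is recorded, so that the third reviewer is not called. This also fits poorly with the blinded evaluator in SAP 2.2.

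The size is unknown. Under the stated assumptions, the extreme case of reviewers always giving way adds 1.6 to 6.9 points. The central example falls to about 2 points, under one subject, if half the false closures fail at the confirmatory visits. The -5.3 points in the downward example might be taken as an equal risk of understating healing. That is not supported, because most of it can be recovered at the next weekly visit.

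Priority is modest. The analysis is descriptive, and closure must also hold at later visits. Against that, the change is cheap, and Protocol 8.5.1 names finding unclear or contradictory protocol text as the pilot's fundamental goal.

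**What to change.** Replace the conferral sentence in Protocol 8.2 with: *The images are sent to the independent reviewer, who records a dated closed/not closed determination before any contact with the Investigator about the case. If it differs from the Investigator's, the third reviewer decides under Section 6.3. The site is told the final determination before Visit 17.*

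Align SAP 2.2 with 6.3, including the third-reader step. Report the number of discordant first reads and the number of overturned closure calls, which would also give the later trial a rate that the present documents lack.

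The reviewers and images stay the same. The costs are routing reads through the sponsor or imaging vendor in the existing window, which can be as short as 5 days (Visit 17 is at 7 ± 2 days), and an IRB-approved amendment for the wording. One limit remains: because only closure calls are reviewed, the reviewer can still infer the Investigator's opinion. The change protects the recorded read from discussion, not from that knowledge.
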